5 STUDY POPULATION

5.1.1 SAMPLE SIZE CALCULATION

Sample size was calculated using the mean overall fit acceptance from the previous pilot BOXER study [REDACTED]

A sample size of 34 is recommended to detect a mean difference between lens Overall fit acceptance of 0.2 units on the 0 to 4 scale using a standard deviation of 0.4 with 80% power and alpha 0.05 in a two-tailed t-test. Therefore, it is recommended that at least 38 subjects are dispensed in the MIKI study, with a target of 34 to complete.

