5.1.2 NUMBER OF PARTICIPANTS

Participants will be screened using CORE records and advertising approved by the UW Office of Research Ethics. Approximately 38 participants will be dispensed with study products in the study, with a target of 34 completing the study.

A documented informed consent process will be conducted with all participants prior to their enrolment in the study and prior to any data collection or measurements.

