5.1.3 INCLUSION AND EXCLUSION CRITERIA

A person is eligible for inclusion in the study if he/she:

1. Is at least 17 years of age and has full legal capacity to volunteer;
2. Has read and signed an information consent letter;
3. Is willing and able to follow instructions and maintain the appointment schedule;
4. Habitually wears soft contact lenses in daily wear, for minimum of 6-months;
5. Is correctable to a visual acuity of 20/40 or better (in each eye) with the study lenses;
6. Has an astigmatism of ≤ 1.00 D in subjective refraction;
7. Can be fit with study contact lenses with a power between -2.00 and -5.00 DS;
8. Demonstrates an acceptable fit with the study lenses;
9. Habitually wears single vision soft contact lenses for at least 8 hours per day, 5 days a week, and is willing to wear contact lenses for at least 12 hours a day in the study.

A person may be excluded from the study if he/she:

1. Is participating in any concurrent clinical or research study;
2. Has any known active* ocular disease and/or infection;
3. Has a systemic condition that in the opinion of the investigator may affect a study outcome variable;
4. Is using any systemic or topical medications that in the opinion of the investigator may affect a study outcome variable;
5. Has known sensitivity to the diagnostic pharmaceuticals to be used in the study;
6. Is pregnant, lactating or planning a pregnancy at the time of enrolment because the associated hormonal changes cause changes in the tear layer which impact contact lens comfort. Verbal confirmation at the screening visit is sufficient;
7. Has undergone refractive error surgery or any intraocular surgery, including cataract surgery;

8. Is an employee of the Centre for Ocular Research & Education;
9. Has participated in the BOXER [REDACTED] or BASSET [REDACTED] Study;
10. Has any history of wearing one of the study contact lenses;
11. Has participated in any clinical trials within a week prior to the study.

* For the purposes of this study, active ocular disease is defined as infection or inflammation, which requires therapeutic treatment. Mild (i.e. not considered clinically relevant) lid abnormalities (blepharitis, meibomian gland dysfunction, papillae), corneal and conjunctival staining and dry eye are not considered active ocular disease. Neovascularization and corneal scars are the result of previous hypoxia, infection or inflammation and are therefore not active.

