12 STATISTICAL ANALYSIS AND DATA MANAGEMENT

12.1 STATISTICAL ANALYSIS

Primary comparisons will be between study lenses, however there are some variables collected over time with the same lens and this time comparison will be analysed (e.g. 'at-home ratings on Days 1, 3 and 5).

All data will be analyzed by CORE at the University of Waterloo. Unmasked data analysis will be conducted using Statistica, SPSS, or other appropriate software. Descriptive statistics will be provided on information regarding baseline variables (age, gender, refractive error distribution, etc.). Table 6 lists the main outcome variables and anticipated statistical procedures. All data will be tested for normality of distribution using Shapiro-Wilk tests.

[figure not shown]

Table 6: Statistical analysis to be conducted

Variable	Analysis	Statistical test
Subjective ratings	Descriptive and other statistics	Mean, Median*, Standard Deviation, Minimum, Maximum, Frequency count
	Effect of treatment on outcome variable within subjects (comparison between study days) Effect of time on ratings (comparison over time)	Friedman Wilcoxon matched pairs test
[REDACTED]	Descriptive statistics	Mean, Median*, Standard Deviation, Minimum, Maximum, Count
	Effect of treatment on outcome variable within subjects (comparison between study days)	RMANOVA Paired t-test

* For non-parametric data only

The critical alpha level for statistical significance will be set at 0.05, with no adjustments for multiple comparisons.

All participants who were evaluated will be included in the analysis, unless their removal is agreed by the sponsor due to protocol deviations and/or adverse events. In the event of missing data, individual data points will not be extrapolated from the collected data.

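### Do the paired between-lens tests wrongly leave out participants graded on only one lens, so that a mixed model is needed?

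*Combined protocol and SAP*

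**What the plan says.** The primary outcome is overall fit acceptance (0 to 4 scale) at the 1-week visit, recorded once per lens period, at Visits 3 and 5 (sections 2 and 5.3). On who is analysed, section 12.1 states "All participants who were evaluated will be included in the analysis, unless their removal is agreed by the sponsor due to protocol deviations"; the same sentence also gives an adverse event as a ground for removal. On missing values it states "In the event of missing data, individual data points will not be extrapolated from the collected data".

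On method, "Table 6 lists the main outcome variables and anticipated statistical procedures". Two sets of tests for the effect of treatment within subjects are visible. For subjective ratings the entry is "Friedman Wilcoxon matched pairs test". For a row whose variable name is redacted it is "RMANOVA Paired t-test".

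Section 5.1.1 sizes the trial for a difference of 0.2 units "using a standard deviation of 0.4 with 80% power and alpha 0.05 in a two-tailed t-test". Section 5.1.2 adds "Approximately 38 participants will be dispensed with study products in the study, with a target of 34 completing the study". Section 9 lets participants who discontinue withdraw their data, and has every discontinuation reported with its reason.

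**The concern.** Paired t and Wilcoxon matched-pairs tests need a value under both lenses, and classical repeated-measures ANOVA and Friedman tests need complete blocks. Someone graded on lens 1 who leaves before the Visit 5 grade counts as evaluated, may appear in the descriptive rows, and drops out of the lens comparison. The same happens when one of two 1-week grades is set aside after a visit-window deviation (section 5.3). No section defines a complete-pair set, so the inclusion sentence and the tests seem to describe different populations.

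Two things would be at stake. Grades already collected would go unused. And if people leave because a lens performed badly, the remaining pairs could give a distorted difference. A mixed model with lens, period, sequence and a random participant effect would use every 1-week grade without imputing any, and so looks like a cheap remedy.

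**Working it through.** **1. The plan's own figure.** Inputs from section 5.1.1: difference 0.2, SD 0.4, two-sided alpha 0.05. For a paired t-test the noncentrality is 0.2/0.4 × √n. Power is 0.795 at n = 33, 0.808 at n = 34 and 0.851 at n = 38. So 34 is reproduced exactly, with 0.4 read as the SD of the within-person difference. Independent groups would need 64 per group. The sample size therefore assumes complete pairs, and 38 − 34 = 4 participants (10.5%) are allowed not to complete.

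**2. Precision gained by using one-lens grades.** The within-person correlation is not in the documents, so it is varied. The SD of the difference is held at 0.4. With 34 pairs the standard error is 0.4/√34 = 0.0686. Generalised least squares with lens, period and sequence terms gives these reductions:

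| Correlation | 34 pairs + 4 first-period only | 36 pairs + 2 |
|---|---|---|
| 0 | 2.7% | 1.3% |
| 0.3 | 1.9% | 0.9% |
| 0.5 | 1.3% | 0.7% |
| 0.7 | 0.8% | 0.4% |

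Power with 34 + 4 moves from 80.8% to between 80.9% (correlation 0.9) and 82.9% (correlation 0).

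**3. How much distortion is possible.** The mean over 38 differs from the mean over 34 by 4/38 of the gap between lost and retained participants. To move the result by the full 0.2, that gap must be 0.2 × 38/4 = 1.9 grades on a 0 to 4 scale.

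**4. Two stopping rules.** The setting is 38 participants, 19 per sequence, with true lens difference 0. In one sequence, 4 participants have a Visit 3 grade and then stop. Both rules are assumptions.

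- Rule A: the 4 with the lowest recorded first-lens grades stop.
- Rule B: the 4 whose second-lens grades would have been lowest stop, so those grades are never recorded.

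Size of the spurious lens difference, by simulation:

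| Correlation | A: pairs | A: mixed model | B: pairs | B: mixed model |
|---|---|---|---|---|
| 0 | 0.043 | 0.003 | 0.043 | 0.049 |
| 0.3 | 0.037 | 0.003 | 0.036 | 0.053 |
| 0.5 | 0.030 | −0.004 | 0.032 | 0.054 |
| 0.7 | 0.024 | −0.002 | 0.023 | 0.045 |

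With 2 stopping, pairs shift by 0.014 to 0.025 under A and 0.014 to 0.026 under B. The mixed model shifts by 0.025 to 0.029 under B. If 4 stop under A, 2 on each lens, the shift for pairs is about 0.

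Under A, stopping depends only on a recorded value, which is the condition the model needs. Under B, those who stop also tend to have low first-lens grades when the correlation is positive. The model adds those low grades to the first lens, while the matching low second-lens grades stay missing, so the contrast tilts further than in the pairs.

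**5. Which rule the schedule suggests.** Section 5.3 says Visit 4 is normally combined with Visit 3. A participant graded on lens 1 therefore usually leaves that visit wearing lens 2, and a later exit may well reflect lens 2 (rule B). Someone who leaves because of lens 1 before Visit 3 has no 1-week grade and enters neither analysis. Rule A needs a participant to be graded on lens 1 and then stop because of it, which is possible but no better supported.

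**The case for a change.** The best case for a change is that it costs almost nothing. With no missing data, the model gives the same standard error as the paired test, and a period term costs about 0.1 point of power. It fills in no values, so the no-extrapolation rule is respected. It also settles in advance what happens to one-lens participants, which matters because section 12.1 describes the analysis as unmasked. The plan does leave this unsaid, and under rule A the model is plainly better.

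Three things weaken the case. First, the advantage reverses under rule B. Second, making a Gaussian model primary sits awkwardly with section 12.1, which tests all data for normality and keeps a non-parametric route; a five-point grade may well fail that test. Whether fit is graded per eye is also not visible, and if it is, the model would need a further term. Third, the row holding the paired t-test has a redacted label and the procedures are only anticipated, so the link to the primary outcome is an inference from the paired sample size.

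The point that the analysis set is unstated survives. The point that the planned test should be replaced does not.

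**Conclusion.** No change follows. The inclusion sentence, the bar on extrapolation, the within-subject tests and the target of 34 completers together lead to one ordinary reading: participants contribute wherever they have data, and the lens comparison uses those with both 1-week grades. The gap is missing detail that analysts fill sensibly, not a contradiction.

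Replacing the paired test by a mixed model is a trade-off. The precision gain is 0.4% to 2.7% of the standard error. The effect on bias is favourable or unfavourable by a few hundredths of a unit, depending on why people stop. In the worst case examined for the paired test, 4 of 38 lost from one sequence, the shift is 0.043, or 22% of the 0.2 target. Balanced losses bring it to about 0 under the rule examined. Power is protected by dispensing to 38. Entry also requires that a participant "Demonstrates an acceptable fit with the study lenses", which makes large fit-related losses less likely.

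This rests on an SD of 0.4 for the difference, one grade per participant per lens, assumed correlations of 0 to 0.7 (0.9 for the lower power figure), and stopping rules that the documents neither confirm nor exclude.

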12.2 DATA MANAGEMENT

Data from this study will be retained by CORE for a minimum of 25 years on a password-protected server. After 25 years, data will be disposed of in accordance with the guidelines laid out by the University of Waterloo.

At the completion of the study CORE will provide a copy of the study data to the sponsor when requested. All data will typically be sent using a secure file share system operated by the University of Waterloo called Sendit which uses 128bit (or 256bit) SSL encryption. This system provides a secure way to transfer files when email is not appropriate, whether because of file size, file type or concerns over security. Sendit includes features such as password protection, a restricted time period for download, IP logging and email notification of download. Files may be encrypted prior to transmission at the request of the sponsor. Using this method means that data files are only stored on University of Waterloo servers until they are downloaded by the sponsor.

12.3 COMMENTS ON SOURCE DOCUMENTS

Data analysis will not be conducted on comments which have been recorded in the source documents, however all comments will be entered into the study database. Only relevant and applicable comments will be included in the final report as deemed necessary by the lead investigator.

13 PROTOCOL TRAINING

All study personnel will be required to complete training prior to their involvement in the study.

14 STUDY MONITORING

Status reports will be provided to the study sponsor by email on a regular basis. Status reports will include:

- The number of participants screened, enrolled, and randomized (i.e. assigned a study ID number), discontinued and completed.
- Details of any protocol deviations.
- Details of any adverse events.

- Reports of unintended events.

Study monitoring visits may be conducted throughout the study and will be scheduled by the study sponsor in conjunction with the lead investigator. In addition study records may be inspected at CORE by the sponsor, the sponsor's designate, the Office of Research Ethics at the University of Waterloo, and by regulatory authorities in Canada and the United States, namely Health Canada and the United States Food and Drug Administration (FDA); however, no records containing identifiable/personal information will be permitted to leave the custody of CORE.

15 STUDY MANAGEMENT

15.1 STATEMENT OF COMPLIANCE

This clinical study is designed to be in compliance with the ethical principles in the Declaration of Helsinki, with the ICH guidelines for Good Clinical Practice (GCP), with the University of Waterloo's Guidelines for Research with Human Participants and with the Tri-Council Policy Statement: Ethical Conduct for Research Involving Humans, 2nd Edition.

- Declaration of Helsinki
- ICH E6 - International Conference on Harmonisation; Good Clinical Practice
- <http://iris.uwaterloo.ca/ethics/human/guidelines/index.htm>
- <http://iris.uwaterloo.ca/ethics/human/ethicsReview/UWStatement.htm>
- <http://www.pre.ethics.gc.ca/eng/policy-politique/initiatives/tcps2-eptc2/Default/>

15.2 ETHICS REVIEW

This protocol will be submitted to and reviewed through the Office of Research Ethics (ORE) at the University of Waterloo. Notification of ethics clearance of the application is required prior to the commencement of the study.

15.3 CLINICAL TRIAL REGISTRATION

This study will be registered with ClinicalTrials.gov by the study sponsor.

15.4 PROTOCOL DEVIATIONS

Protocol deviations are unanticipated or unintentional changes to a study after it has received prior sponsor approval and ethics clearance. Protocol deviations can be major or minor.

15.4.1 MAJOR PROTOCOL DEVIATIONS

Major protocol deviations may impact the research protocol, information consent document or other study materials, usually cannot be anticipated ahead of time and are often necessary to ensure the safety and welfare of the participants.

The following are examples of protocol deviations that must be reported to the ORE:

- Changes in procedures initiated to eliminate immediate risks/hazards to participants;
- Enrollment of participants outside the protocol inclusion/exclusion criteria whether agreed to or not by the sponsor;
- Medication / device / intervention errors (i.e. incorrect drug or dosage of drug / incorrect contact lens(es) dispensed / incorrect care system dispensed);
- Inadvertent deviation in specific research intervention procedures or timing of the research intervention which could impact upon the safety or efficacy of the study-related intervention or upon the experimental design;
- Information consent documentation violations: no documentation of informed consent; incorrect version of, or incomplete, informed consent documentation used.

15.4.2 MINOR PROTOCOL DEVIATIONS

Protocol deviations caused by or which originate with research participants are considered minor, and normally are not reported to the ORE unless these result in increased risk to the participant(s). The following are examples of protocol deviations that are considered minor and do not require reporting to the ORE:

- Logistical or administrative aspects of the study (e.g., study participant missed appointment, change in appointment date);
- Inadvertent deviation in specific research intervention procedures or timing of the research intervention which would not impact upon the safety or efficacy of the study-related intervention or upon the experimental design (i.e., missing a measurement during a session that is not considered critical for the study).

15.4.3 REPORTING AND DOCUMENTING PROTOCOL DEVIATIONS

Major protocol deviations must be reported to the ORE within 7 days of the deviation occurring (or its discovery) using the Protocol Deviation Report Form 107 (PDRF). Information from the PDRF is provided to the Clinical Research Ethics Committee (CREC) at the next monthly meeting.

All protocol deviations (major and minor) occurring during the study will be documented and included in the final report.

15.5 PREMATURE TERMINATION OF THE STUDY

The sponsor, CORE or the Office of Research Ethics at the University of Waterloo may terminate the study at any time for any reason.

15.6 STUDY PARTICIPANT RECORDS

Study participant records will be completed to comply with GCP guidelines. Records will contain:

- Unique study acronym and/or code;
- Participant ID;
- Date enrolled;
- Confirmation by investigator that participant met eligibility criteria;
- Confirmation that participant received a signed and dated copy of informed consent;
- Exit date;
- Investigator's signature confirming study exit.

15.7 RETENTION OF STUDY RECORDS AND DATA

Records and data from this study will be retained for a minimum of 25 years. Details regarding storage procedures are given in CORE SOP014_v01_Clinical data management.

16 REPORT

A report will be sent to the sponsors according to terms described in the study contract.

